8.2.3 Frequency of Sickle Cell Disease–Related Complications

SCD-related complications over the course of the treatment period will be recorded as adverse events for each participant. SCD-related complications may include the following: sickle cell anemia with crisis, ACS, pneumonia, priapism, splenic sequestration, hepatic sequestration, stroke, leg ulcers, dactylitis, and osteonecrosis. SCD-related complications will be summarized in the SCD-related adverse event summaries as described in Section 8.2.2.

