4. STUDY ENDPOINTS

Safety:

• Treatment-emergent adverse events (TEAEs) and serious adverse events (SAEs)

Sickle Cell Disease-Related Complications:

• Frequency of SCD-related complications

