5. DEFINITIONS AND TERMINOLOGY

Study Day

Study Day is defined relative to initiation of treatment, i.e., Day 1. Thus, the study day of an event is calculated as:

$$Study Day = event date - Day 1 date + 1.$$

Study Visit

Study Visit is the nominal visit as recorded on the Case Report Form (CRF).

Change from Day 1

Change from Day 1 to follow-up visit will be calculated as Day 1 subtracted from the follow-up measurement for all assessments. Percent change from Day 1 values to post-Day 1 values will be calculated using the following formula where applicable:

Exposure to Study Drug

Duration of exposure to study drug is defined as the number of weeks from Day 1 to the last date of dosing of study drug. The derivation is as follows:

(Last dose date - First dose date
$$+ 1$$
)/7

Actual exposure to study drug is defined as the number of weeks from Day 1 to the last date of dosing of study drug which excludes days where treatment was entirely missed or intermittently stopped as recorded in the CRF. The derivation is as follows:

(Last dose date - First dose date - Number of days study drug was not taken +1)/7

Concomitant Medications

Concomitant medications are those medications taken on or after the initiation of study drug. This definition includes medications started prior to the initiation of study drug, but continuing concurrently with study drug.

Red blood cell (RBC) transfusions are collected on a separate CRF.

Treatment-Emergent Adverse Event

A TEAE is defined as an AE that emerges on or after initiation of study drug (having been absent pre-treatment), or an AE that existed pre-treatment and worsened on treatment (relative to the pre-treatment state) through 28 days after study drug discontinuation. AEs occurring on Day 1 are assumed to be treatment-emergent.

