8.2 Safety

8.2.1 Summary of Exposure

The duration of study drug exposure and actual study drug exposure will be summarized with descriptive statistics.

The number and percentage of participants who permanently discontinued study drug, and the reason for discontinuation (AE or other) will be summarized as collected on the study drug administration CRF. The number and percentage of participants who missed at least 1 dose of study drug or had at least 1 dose reduction will be summarized. The summary will include the number and percentage of participants who had a dose reduction or dose missed due to an adverse event or other reason. Additionally, the number and percentage of participants will be summarized in categories of number of missed doses and number of dose reductions.

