8.2.2 Adverse Events

All AEs will be coded using MedDRA (current version). Adverse events reported for participants participating in this study will be graded using the National Cancer Institute's (NCI) Common Terminology Criteria for Adverse Events (CTCAE), version 5.0. For AEs not adequately addressed in the NCI CTCAE, version 5.0, protocol-specified criteria will be used.

All adverse events summaries described below will be presented for both non-SCD and SCD-related TEAEs.

Non-SCD-related TEAE summary tables will exclude SCD related events including but not limited to the preferred terms of: sickle cell anemia with crisis, acute chest syndrome (ACS), pneumonia, priapism, splenic sequestration, hepatic sequestration, stroke, leg ulcers, dactylitis, and osteonecrosis. Additional TEAE tables will summarize the aforementioned SCD related events.

Overall summaries will be presented which include the number of TEAEs and the number and percentage of participants who experienced at least one TEAE. The summaries will also include TEAEs Grade 3 or greater, TEAE related to study drug, TEAEs leading to study drug reduction, TEAEs leading to study drug interruption, TEAEs leading to discontinuation of study drug, and SAEs. TEAEs leading to deaths will be summarized together regardless if they are SCD-related, as cause of death may include multiple TEAEs.

Additional summaries of TEAEs will be provided showing the number and percentage of participants who experienced at least one TEAE. These summaries will be presented by MedDRA System Organ Class (SOC), Preferred Term (PT) and maximum severity. If a participant reports the same PT multiple times within the same SOC, that PT will only be counted once within that SOC for that participant. As with the PT, if a participant reports multiple conditions within the same SOC, that SOC will only be counted once for that participant.

The occurrence of TEAEs assessed as related to voxelotor by the investigator will be tabulated by SOC, PT, and maximum severity. Serious adverse events will be presented by SOC, PT, and maximum severity.

Grouped terms for rash and abdominal pain will be summarized.

Adverse events recorded in the CRF which began prior to first dose of study drug will not be included in the summary tables.

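### By complication, the frequency endpoint is only a percentage of participants with at least one event, so under open-ended follow-up it mixes event rate with time on study

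*SAP*

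**What the plan says.** SAP section 4 lists two endpoint groups: adverse events, and "Frequency of SCD-related complications". For the second, SAP 8.2.3 only points elsewhere: "SCD-related complications will be summarized in the SCD-related adverse event summaries as described in Section 8.2.2".

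SAP 8.2.2 applies one set of tables to both kinds of event: "All adverse events summaries described below will be presented for both non-SCD and SCD-related TEAEs". They work at two levels:

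- **Overall.** "Overall summaries will be presented which include the number of TEAEs and the number and percentage of participants who experienced at least one TEAE". Repeat events enter here, with all SCD-related events pooled.
- **By system organ class and preferred term.** These tables separate crisis, acute chest syndrome, stroke and the rest. They give the number and percentage of participants with at least one event, by maximum severity. "If a participant reports the same PT multiple times within the same SOC, that PT will only be counted once within that SOC".

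Exposure is handled separately in SAP 8.2.1: "The duration of study drug exposure and actual study drug exposure will be summarized with descriptive statistics". It is not used as a denominator for events. Protocol 8.4.3 likewise has complications summarised in the same way as TEAEs and mentions no rate.

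Under Protocol 3.2, treatment may continue for as long as the investigator judges that benefit outweighs risk, or until the participant can get voxelotor from another source. No common follow-up length is set.

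**The concern.** The proportion of participants with at least one event rises with follow-up even when the event rate is constant. When follow-up differs between participants, the proportion cannot be read as a frequency. Two groups with the same rate will show different percentages if one was followed longer, and a group with a lower rate can show the higher percentage. For recurrent events such as painful crises, which Protocol 1.1 describes as recurrent, the by-complication table also drops every event after a participant's first.

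One side-by-side display is planned: SAP 8.2.2 groups adverse events in the modified-dose subset by dosing form before the switch. Interim cuts (SAP 6.3) and splits by antecedent study (Protocol section 8) are optional. In any of these, unequal follow-up could be mistaken for a difference in complication frequency.

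**Working it through.** The plan states no event rate, follow-up distribution or precision figure for this endpoint, so there is no figure of its own to reproduce. The check has two parts.

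**1. What can be recovered from the planned tables.** For all SCD-related events pooled, the overall event count could be set against the exposure summary to give a crude rate. For a single complication only the participant count is available, so no rate can be formed.

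**2. How far the percentage moves with follow-up.** Let r be events per person-year and T = weeks / 52.1775.

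- Poisson: P(at least one) = 1 − exp(−rT).
- Negative binomial, dispersion 1: P(at least one) = 1 − 1/(1 + rT).
- Share of events missing from the by-term count = 1 − P(at least one)/(rT).

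The only rate taken from the documents is stroke at 1.02% per year (Protocol 1.1, ages 2 to 5). The crisis rates, the dispersion and the follow-up of 48 and 144 weeks are assumptions. T is 48/52.1775 = 0.920 and 144/52.1775 = 2.760 years.

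| Same true rate | Model | 48 weeks | 144 weeks |
|---|---|---|---|
| Stroke, 0.0102/year | Poisson | 0.9% | 2.8% |
| Crisis, 0.5/year | Poisson | 36.9% | 74.8% |
| Crisis, 1/year | Poisson | 60.1% | 93.7% |
| Crisis, 1/year | Negative binomial | 47.9% | 73.4% |
| Crisis, 2/year | Poisson | 84.1% | 99.6% |

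*Rank reversal.* Half the rate with three times the follow-up gives the higher percentage:

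- Crisis, 0.5/year over 144 weeks against 1/year over 48 weeks: 74.8% against 60.1% (Poisson), 58.0% against 47.9% (negative binomial).
- Stroke, 0.51% per year over 144 weeks against 1.02% per year over 48 weeks: 1.4% against 0.9%.

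*Events not shown.* At 1 crisis per year (Poisson), 1 − 0.601/0.920 = 35% of events are missing from the by-term count at 48 weeks, and 1 − 0.937/2.760 = 66% at 144 weeks. For stroke the shares are 0.5% and 1.4%, so this part matters only for recurrent events.

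*Effect in a single pooled table.* Take 600 participants at 1 event per year, half followed for 24 weeks and half for 240. About 1518 events appear as about 408 participants (67.9%). The same person-time spread evenly, 132 weeks each, gives 92.0%.

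**Interval for a rate.** In 20,000 simulated samples of 100 participants (1 event per year, dispersion 1), the estimated rate averaged 1.00 per year at both follow-up lengths. A nominal 95% exact Poisson interval covered 84.5% at 48 weeks and 69.3% at 144 weeks. A robust log-scale interval covered 94.4% and 94.2%.

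**Time origin for the modified-dose groups.** Suppose a switch at week s, 48 further weeks of treatment and the 28-day tail. Counting from first dose would make s/(s + 52) of person-time pre-switch: 12/64 = 18.8%, 24/76 = 31.6% or 48/100 = 48.0% for a switch at Week 12, 24 or 48.

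**The case against.** The best defence is that this is an enhancement to a descriptive study. Both documents use the word frequency for a count in a category, the SAP does what Protocol 8.4.3 asks, and no test or decision depends on the result. AE and dosing dates are collected, so a rate could be added at reporting. The SAP also promises additional tables of SCD-related events without naming their statistic. The one planned group display does not mention complications specifically, and nothing in the documents points to threefold follow-up differences there. The illustrations rest on assumed rates and durations, and the documented stroke rate is a peak for young children while the study also includes participants aged 12 and over.

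Much of this is fair, and it limits the consequence to interpretation. It does not make the by-complication percentage interpretable when follow-up is open-ended, and a rate that could be added later is not a planned one. The assumed values set the size of the distortion, not its direction.

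Some objections to the remedy also stand. A robust interval fails with few events: at 20 participants, 48 weeks and 0.05 events per year (assumed), it covers only about 54%, against about 98% for exact Poisson. A rule for sparse data is therefore needed. Counting AE records leaves the result open to differences in how sites split one crisis into several records. SAP 8.2.3 speaks of the treatment period, whereas the tables it cites use the TEAE window, so the text should name one window.

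**Conclusion.** The concern holds. For each complication the plan gives only participants with at least one event, with no event count and no person-time rate, although follow-up is open-ended and some complications recur. At an assumed 1 crisis per year, tripling follow-up from 48 to 144 weeks moves the percentage by 33.6 points under Poisson (93.7 − 60.1) and 25.5 points under negative binomial (73.4 − 47.9), with no change in rate. For stroke at the protocol's background rate the shift is 1.9 points (2.8 − 0.9). These are illustrations under assumed follow-up, crisis rates and dispersion, not predictions for this trial. The SAP does not depart from the protocol, and no error rate or sample size is touched. It should be fixed because a stated endpoint is hard to interpret as planned and the remedy is cheap.

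**What to change.** In SAP 8.2.3, for all SCD-related complications together and for each listed one, add the number of events, person-years, and events per 100 person-years with a 95% confidence interval. Keep the percentage tables. Specify:

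- **Window.** Use the TEAE window, which runs "through 28 days after study drug discontinuation", for both events and person-time: first dose to the earliest of last dose plus 28 days, end of follow-up or data cut.
- **Person-time.** Build it on the first of the two exposure definitions in SAP section 5: "Duration of exposure to study drug is defined as the number of weeks from Day 1 to the last date of dosing". Do not use actual exposure, which removes missed days, because events starting on those days still count as TEAEs.
- **Event unit.** One AE record with its own start date, the unit behind the overall TEAE count.
- **Interval.** Robust or negative binomial, with exact Poisson when events are sparse. Set the cut-off in advance.
- **Modified-dose groups.** Start events and person-time at the switch date, which Protocol 5.1 has recorded on the dosing eCRF. State how a partial AE date in the switch month is treated, because SAP 6.2.2 imputes a missing day to the start of the month or to treatment start.

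The cost is SAP wording, a few table columns and some programming. AE start dates, dosing dates and the switch date are already collected, and Protocol 7.2.4 provides for extra data on SCD-related events. The plan stays descriptive; SAP 8.4 already reports a 95% interval for PK.

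Three caveats belong with the rates. A pooled rate assumes roughly constant risk, whereas Protocol 1.1 says stroke risk varies with age. Leaving the study may be informative, since it depends partly on judged benefit. Event counts depend on how sites record separate crises.

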8.2.4 Concomitant Medications

Concomitant medications will be coded using the World Health Organization (WHO) Drug Dictionary (current version) and summarized to the therapeutic drug class, Anatomical Therapeutic Chemical (ATC) 2 classification, and preferred name.

8.2.5 Clinical Laboratory Assessments

The following protocol-specified clinical laboratory findings will be summarized using descriptive statistics.

- 1. Hematology:
 - a. Hemoglobin (Hb)
 - b. Neutrophils (absolute and %)
 - c. Platelets
 - d. Reticulocyte count (percent and absolute reticulocyte)
 - e. White blood cells (WBCs)
- 2. Chemistry and Liver Function Tests:
 - a. Alkaline phosphatase
 - b. Alanine aminotransferase (ALT)
 - c. Aspartate aminotransferase (AST)
 - d. Potassium
 - e. Indirect bilirubin
 - f. Total bilirubin
 - g. Lactate dehydrogenase (LDH)
 - h. Serum Erythropoietin

Change from Day 1 and the percent change from Day 1 will be summarized for the above laboratory results. Analyte units will be converted to International System of Units (SI). The end-of-treatment assessments performed upon completion of the antecedent study may serve as the Day 1 assessments for Study GBT440-038.

Participant listings of laboratory data will include a separate listing for clinically significant laboratory results.

If indirect bilirubin is missing and direct and total bilirubin are collected, indirect can be calculated as:

 $Indirect \ Bilirubin = Total \ Bilirubin - Direct \ Bilirubin.$

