6.10. Clinical Laboratory Assessments

Blood and urine samples for clinical laboratory tests will be collected at the time points indicated in the Schedule of Assessments (Appendix A).

The clinical laboratory tests that will be performed are listed in Table 9. All tests will be performed at the local clinical laboratory.

Table 9: Clinical Laboratory Tests

He	matology	Serum Chemistry Other
_	Hematocrit	 Alanine aminotransferase Urine pregnancy test ^a
_	Hemoglobin	- Albumin ^b
_	Mean corpuscular hemoglobin	 Alkaline phosphatase
	concentration	 Aspartate aminotransferase
-	Mean corpuscular volume	- Bicarbonate b, c
_	Platelet count	Bilirubin (total, direct, and
_	RBC count	indirect)
_	RBC distribution width	- Blood urea nitrogen
_	Reticulocyte count	- Calcium ^b
	(absolute and percent)	- Chloride ^b
_	WBC count with differential	- Creatinine
	(basophils, eosinophils,	- Glucose ^b
	neutrophils, monocytes,	 Lactate dehydrogenase
	lymphocytes)	- Potassium ^b
		- Sodium ^b

Abbreviations: RBC, red blood cell; WBC, white blood cell.

It is the responsibility of the Investigator or designee to assess the clinical significance of all abnormal clinical laboratory values as defined by the list of normal values on file for the local clinical laboratory. All clinically significant laboratory value abnormalities are to be recorded as AEs.

Additional and repeat clinical laboratory tests for the evaluation of abnormal results and/or AEs during the study may be performed at the discretion of the Investigator or upon request of the sponsor.

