6.10.2. Total Blood Volume

On-study blood volume collections will not exceed 2.4 mL/kg in any given 4-week period. Specific blood specimens (eg, exploratory measures) may be omitted at the discretion of the

^a For female participants of childbearing potential.

^b Only record on the CRF if the laboratory value is abnormal and considered clinically significant by the Investigator.

^c After implementation of Amendment 2 record bicarbonate values only; if the local laboratory only provides carbon dioxide values, do not record on the CRF.

Investigator, if warranted, such as in the context of blood loss associated with standard clinical care or bleeding events, or if otherwise deemed appropriate.

Due to total volume restrictions in pediatric research, assessments will be prioritized as indicated in Table 10.

Table 10: Priority of Study Assessments

Priority	Test
1	Hematology
2	Serum chemistry

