8.4.2. Clinical Laboratory Tests and Vital Signs

Clinical laboratory test and vital sign results over time will be summarized using descriptive statistics.

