Appendix A. SCHEDULE OF ASSESSMENTS

Study Day/Week	Treatment Period								EOS
	First 48 Weeks					After Week 48			+7 days c
	Day 1 a	Week 12 b ± 5 days	Week 24 ± 10 days	Week 36 b ± 10 days	Week 48 ± 10 days	Q12Wk ± 10 days	Q24 Wk ± 10 days	Q48 Wk ± 10 days	
Informed Consent/Assent	X								
Review Inclusion/Exclusion Criteria	X								
Medical History	X								
Weight and Height d	X		X		X			X	
Abbreviated Physical Examination ^e	X				X				
Vital Signs ^f	X	X	X	X	X		X	X	X
Adverse Events	X	X	X	X	X		X	X	X
Concomitant Medications	X	X	X	X	X		X	X	X
Hematology ^g	X	X	X	X	X		X	X	X
Serum Chemistry h	X		X		X			X	X
Urine Pregnancy Test i	X	X	X	X	X		X	X	X
Taste and Palatability Questionnaire with InClinic Dosing ^j	Performed on Day of Switch, and at the following two consecutive visits								
Transcranial Doppler k	Performed as standard of care								
Study Drug Dispensing and Accountability ¹	X	X	X	X	X	X	X	X	X

Abbreviations: CRF, case report form; EOS, End of Study; Q12Wk, every 12 weeks; Q24 Wk, every 24 weeks; Q48 Wk, every 48 weeks; TCD, transcranial Doppler.

Study Day/Week	Treatment Period					EOS			
	First 48 Weeks			After Week 48			+7 days ^c		
	Day 1 ^a	Week 12 b ± 5 days	Week 24 ± 10 days	Week 36 b ± 10 days	Week 48 ± 10 days	Q12Wk ± 10 days	Q24 Wk ± 10 days	Q48 Wk ± 10 days	

Voxelotor

GBT440-038

- a. Day 1 assessments will be performed prior to dosing. If any of the Day 1 assessments were performed at the last study visit in the originating (parent) clinical study, and the Day 1 visit occurs on the same date, the tests do not need to be repeated.
- b. Week 12 and Week 36 planned visits for participants who roll over to this study from Study GBT440-042 will be for drug dispensing, collection of adverse events and concomitant medications only.
- c. The EOS visit should be conducted 4 weeks (28 days) after the last dose of study drug (+7-day window).
- d. Height and weight will be collected only for participants < 18 years of age.
- e. Will include general appearance; examination of eyes, skin, cardiovascular system, and respiratory system; abdominal examination; and a symptom-directed examination.
- f. Heart rate and blood pressure will be measured after participant has rested for ≥ 5 minutes in the seated or supine position. If the first vital sign measurement is outside the normal range and deemed clinically significant, the measurement will be repeated within 5 minutes.

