- g. Will include the following: hematocrit, hemoglobin, mean corpuscular hemoglobin concentration, mean corpuscular volume, platelet count, red blood cell distribution width, reticulocytes (absolute and percent), and white blood cell count with differential.
- h. Will include the following: alanine aminotransferase, albumin, alkaline phosphatase, aspartate aminotransferase, bilirubin (total, direct, and indirect), blood urea nitrogen, creatinine, lactate dehydrogenase. Laboratory values for bicarbonate, calcium, chloride, glucose potassium, and sodium should only be recorded on the CRF if the laboratory value is abnormal and considered clinically significant by the Investigator).
- i. Will be performed for female participants of childbearing potential only. If the urine pregnancy test is positive, the result must be confirmed per local standard of care (eg, ultrasound or serum pregnancy test).
- j. Upon introduction of a new dosage form (either powder for oral suspension or dispersible tablets) or switch to higher dose (ie, modified dispersible tablet) to participants, a brief questionnaire will be administered to parents and/or children (aged ≥ 5 years) during the first visit when the transition is made and at the subsequent 2 scheduled visits.
- k. For all participants, results from TCD assessments performed as part of standard of care at each site will be recorded on the CRF.
- 1 Voxelotor will be dispensed in 12-week (~90-day) intervals with instruction to participants to return any used/unused bottles/stick packs to the clinic. At the Day 1 Visit, only study drug dispensing will be performed. At the EOS visit, only study drug accountability will be performed.

APPENDIX B. SCHEDULE OF ASSESSMENTS FOR SELECT SITES PARTICIPATING IN VOXELOTOR PLASMA AND WHOLE BLOOD PK COLLECTIONS UPON SWITCHING TO THE MODIFIED DOSE DISPERSIBLE TABLETS ^a

Study Day/Week	Day of Switch	14 Days Post-Switch	12 Weeks Post-Switch
PK Sample Collection (plasma and whole blood)	X	X	X
	(Predose)	(Predose)	(Predose)
Other Assessments	Per Scheduled Visit on Day of Switch (Appendix A) and must include Safety Assessments ^b Concomitant Medications Update	Safety Assessments ^b Concomitant Medications Update	Safety Assessments ^b Concomitant Medications Update
Taste and Palatability Questionnaire	X	X	X

Abbreviations: PK, pharmacokinetic.

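### The laboratory list in SAP 8.2.5 does not match what the protocol collects: it includes serum erythropoietin, which is not scheduled, and omits creatinine, blood urea nitrogen and direct bilirubin, which are

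*SAP*

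**What the plan says.** SAP 8.2.5 opens with "The following protocol-specified clinical laboratory findings will be summarized using descriptive statistics". The chemistry part has eight items: alkaline phosphatase, ALT, AST, potassium, indirect bilirubin, total bilirubin, LDH and, as item 2h, "Serum Erythropoietin". Change and percent change from Day 1 are planned for every item. The same section adds: "Participant listings of laboratory data will include a separate listing for clinically significant laboratory results".

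On collection, protocol 6.10 states: "The clinical laboratory tests that will be performed are listed in Table 9". The chemistry row of Appendix A ("Serum Chemistry h") is marked at Day 1, Week 24, Week 48, every 48 weeks after that, and End of Study. Its footnote h includes "bilirubin (total, direct, and indirect), blood urea nitrogen, creatinine, lactate dehydrogenase" with no limit on recording. Table 9 note b limits some other analytes: "Only record on the CRF if the laboratory value is abnormal and considered clinically significant by the Investigator".

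On analysis, protocol 8.4.2 says "Clinical laboratory test and vital sign results over time will be summarized using descriptive statistics" and excludes no analyte. The SAP Introduction states that its methods replace those in the protocol where applicable, so the shorter SAP list governs.

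**The concern.** The SAP describes its list as coming from the protocol, yet the two differ in both directions. One listed analyte has no scheduled sample, and three analytes sampled throughout are not summarised. No reason is given for either.

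This is a long-term safety study with no fixed treatment duration, and its objective names clinical laboratory tests among the parameters on which safety will be assessed. Protocol 1.1 describes the disease partly by progressive damage to organs. Creatinine and blood urea nitrogen are the only renal chemistry measures scheduled. Direct bilirubin is the conjugated fraction, and Table 6 counts its elevation among the signs of compromised liver function. If the SAP is followed as written, the report will contain no table showing how any of these three moved over time in the group.

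**Working it through.** No sample size, power or error rate bears on this point. The check is a comparison of lists.

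**Step 1. What is always recorded.** Table 9 has 16 serum chemistry analytes, counting the three bilirubin fractions separately. Note b restricts 7 of them: albumin, bicarbonate, calcium, chloride, glucose, potassium and sodium. That leaves 16 − 7 = 9 recorded at every chemistry visit.

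**Step 2. Match against SAP 8.2.5.**

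| Analyte | Recorded under Table 9 | Summarised in SAP 8.2.5 |
|---|---|---|
| Alkaline phosphatase | Always | Yes |
| ALT | Always | Yes |
| AST | Always | Yes |
| Total bilirubin | Always | Yes |
| Indirect bilirubin | Always | Yes |
| LDH | Always | Yes |
| Direct bilirubin | Always | No |
| Blood urea nitrogen | Always | No |
| Creatinine | Always | No |
| Potassium | Only if abnormal and clinically significant | Yes |
| Serum erythropoietin | Not in Table 9 | Yes |

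Six of the 9 always-recorded measures are summarised and 9 − 6 = 3 are not. Both scheduled renal measures (2 of 2) are among the three. Of the SAP's 8 chemistry rows, 6 rest on a complete scheduled series and 8 − 6 = 2 do not.

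Albumin is a small uncertainty in the count. Note b restricts it, but Appendix A footnote h does not place it among the restricted analytes. If footnote h governs, the figure is 6 of 10. The conclusion does not change.

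**Step 3. Erythropoietin.** SAP item 2h is its only mention in either document. It is absent from Table 9, from Appendix A footnotes g and h, and from Appendix B. SAP 8.2.5 lets end-of-treatment results from the antecedent study stand as Day 1, so a Day 1 value might exist. Change from Day 1 = follow-up value − Day 1 value, and the current protocol schedules no follow-up value.

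**Step 4. Potassium.** Under note b a normal follow-up value is not entered. A visit mean therefore describes only participants whose value was abnormal and judged clinically significant. Change from Day 1 needs two recorded values. If Day 1 is also recorded under note b, it exists only for participants who met that condition twice.

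**Step 5. How much of direct bilirubin can be recovered.** SAP 8.2.5 uses indirect = total − direct, so direct = total − indirect. Means are additive, so when the same participants contribute both measures at a visit, mean direct = mean total − mean indirect. The same holds for mean change. The SD, median, minimum, maximum and percent change cannot be obtained from the planned tables. Creatinine and blood urea nitrogen have no such identity, so nothing about them can be recovered.

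**The case against.** The strongest reply is that safety information on these analytes is not lost. Protocol 6.10 and Section 7 require clinically significant laboratory abnormalities and changes from baseline to be recorded as adverse events, and SAP 8.2.2 tabulates treatment-emergent events by system organ class, preferred term and maximum severity. Those events, not laboratory values, are the stated safety endpoint. SAP 8.2.5 also plans participant laboratory listings. Table 6 applies conjugated bilirubin to individual participants, which a missing group table does not affect. All of this stands. A reader might infer that renal function and conjugated bilirubin disappear from the safety results; the documents do not support that. The adverse event route does not cover a gradual group shift in which no single value is judged clinically significant, and a listing does not display one.

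Second, the SAP list is visibly a selected panel: it also omits haematocrit, red cell count and the red cell indices. A sponsor may choose a subset. But other haematology rows, including haemoglobin and reticulocytes, are kept, whereas both renal measures are gone and no reason is given.

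Third, a reader might infer that erythropoietin was never collected and that its table must be empty. Table 9 note c shows that laboratory recording changed at Amendment 2, and neither the CRF nor earlier protocol versions are available here. The documents support only that it is not in the current schedule. The request should therefore be to delete it or state its source.

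**Conclusion.** The point holds as a mismatch between the SAP's summary list and the protocol's data collection. No summary over time is planned for either scheduled renal measure or for direct bilirubin: 6 of 9 always-recorded chemistry measures are summarised. Two of the 8 chemistry rows that are planned lack a usable series: erythropoietin has no scheduled follow-up sample, and potassium is selectively recorded. The loss is the group-level view of gradual change, complete for creatinine and blood urea nitrogen and partial for direct bilirubin. The study's validity is not in question. It is a clear and cheap correction that should be made before the tables are produced.

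This rests on two assumptions. The first is that the SAP list is exhaustive for summaries, which is how it reads. The second is that Table 9 and Appendix A govern collection. Appendix C says liver function tests are not a routine safety procedure in this study, which conflicts with the scheduled ALT, AST and bilirubin and should be reconciled.

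**What to change.** In SAP 8.2.5:

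- Delete serum erythropoietin, or state in which study, at which visits and under which protocol version it is collected.
- Add creatinine, blood urea nitrogen and direct bilirubin, with value, change and percent change from Day 1 by visit.
- Move potassium to a listing, or state beside its summary that only abnormal, clinically significant values are recorded.

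A shift table against reference ranges is not required. Protocol 10.3 says that reference ranges are supplied to the sponsor as appropriate. It does not say that they are age-specific or held in the study database, and all tests are run locally at up to approximately 70 sites.

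The cost is a wording change and a few more table rows. The three added analytes are already recorded, so no samples, visits or protocol amendment are needed.
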